6.1.3 Relationship to Study Drug

The investigator will use the following definitions to assess the relationship of the adverse event to the use of study drug:

Reasonable Possibility	An adverse event where there is evidence to suggest a causal relationship between the study drug and the adverse event.
No Reasonable Possibility	An adverse event where there is no evidence to suggest a causal relationship between the study drug and the adverse event.

For causality assessments, events assessed as having a reasonable possibility of being related to the study drug will be considered "associated." Events assessed as having no reasonable possibility of being related to study drug will be considered "not associated." In addition, when the investigator has not reported a causality or deemed it not assessable, AbbVie will consider the event associated.

If an investigator's opinion of no reasonable possibility of being related to study drug is given, an Other cause of event must be provided by the investigator for the serious adverse event.

[figure not shown]

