11.2 Analysis of Adverse Events

11.2.1 Treatment-Emergent Adverse Events

Treatment-emergent AEs will be summarized separately for the DB placebo-controlled period and for the DB/OL period of Any Adalimumab.

Treatment-emergent AEs during placebo-controlled DB period are defined as events that begin or worsen either on or after the first dose of study drug and up to the first dose of

study drug at Week 4, or within 70 days after the last dose of study drug, or the date subjects initiate adalimumab therapy not supplied in the context of Study M14-233, for subjects who discontinued prior to Week 4. Treatment-emergent AEs during DB/OL period of Any Adalimumab are defined as events that begin or worsen either on or after the first dose of adalimumab in DB or OL period, and within 70 days after the last dose of study drug, or the date subjects initiate adalimumab therapy not supplied in the context of Study M14-233.

An overview of treatment-emergent AEs, including AEs of special interest such as adverse events leading to death and adverse events leading to early termination, AEs by Medical Dictionary for Drug Regulatory Activities (MedDRA version 20.0 or later) preferred term and system organ class, AEs by maximum relationship to study drug, and AEs by maximum severity will be summarized by number and percentage.

The number and percent of subjects experiencing treatment-emergent adverse events will be summarized for the following adverse event categories. Comparisons of the percent of subjects experiencing an adverse event between adalimumab and placebo during the DB placebo controlled period will be performed using Fisher's exact tests. Only P values < 0.100 when rounded to three digits will be presented.

- Any treatment-emergent adverse event.
- Any treatment-emergent adverse event with a Reasonable Possibility of being related to study drug by the investigator.
- Any treatment-emergent severe adverse event.
- Any treatment-emergent serious adverse event.
- Any treatment-emergent adverse event leading to discontinuation of study drug.
- Any treatment-emergent adverse event leading to death.
- Any treatment-emergent adverse event of special interest.
- Any deaths.

Adverse events with missing or unknown relationship to study drug will be categorized as having a reasonable possibility of being study drug-related. Adverse events with missing or unknown severity will be categorized as severe.

Treatment-emergent adverse events will be summarized as follows:

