
- Grouped by System Organ Class and Preferred Term.
- A by-subject listing will be provided.
- Grouped by System Organ Class, Preferred Term and maximum Severity.
- Grouped by System Organ Class, Preferred Term and maximum Relationship to Study Drug.
- Grouped by System Organ Class and Preferred Term with subject numbers.

Treatment-emergent AEs occurring for more than 5% of the subjects in any of the treatment arms will be summarized by MedDRA PT in decreasing frequency of adalimumab treatment arm.

In treatment-emergent AE tables, a subject who reports more than one treatment-emergent AE in different system organ classes will be counted only once in the overall total. A subject who reports two or more different preferred terms which are in the same SOC will be counted only once in the SOC total. A subject who reports more than one treatment AE with the same preferred term will be counted only once for that preferred term using the most extreme incident (i.e., most "severe" for the severity tables and most "related" for the relationship tables).

Adverse events will also be summarized by maximum severity. If a subject has an adverse event with unknown severity, then the subject will be counted in the severity category of "unknown," even if the subject has another occurrence of the same adverse event with a severity present. The only exception is if the subject has another occurrence of the same adverse event with the most extreme severity – "Severe." In this case, the subject will be counted under the "Severe" category.

Adverse events will also be summarized by maximum relationship to study, as assessed by the investigator. If a subject has an adverse event with unknown relationship, then the subject will be counted in the relationship category of "unknown," even if the subject has another occurrence of the same adverse event with a relationship present. The only exception is if the subject has another occurrence of the same adverse event with a relationship assessment of "Reasonable Possibility." In this case, the subject will be counted under the "Reasonable Possibility" category, respectively.

Treatment-emergent AEs will be summarized for any adalimumab set by event rate per 100 patient-years, defined as

$$100 \times \frac{\text{Number of TEAEs}}{\text{Total Patient Years}}$$

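### SAP 11.2.1 codes adverse events of unknown severity or relationship as severe or related in one place and as unknown in another, so its tables may disagree

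*SAP*

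**What the plan says.** SAP 11.2.1 lists the overview categories, which include severe events and events with a reasonable possibility of being related. Directly after that list come two coding rules: "Adverse events with missing or unknown relationship to study drug will be categorized as having a reasonable possibility of being study drug-related", and "Adverse events with missing or unknown severity will be categorized as severe". Neither is limited to a particular table. The next sentence introduces the list of further summaries, which includes those by maximum severity and by maximum relationship.

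Later in the same section, the paragraph on maximum severity says: "If a subject has an adverse event with unknown severity, then the subject will be counted in the severity category of" unknown, even where another occurrence of the same event has a recorded severity. It then allows one override: "The only exception is if the subject has another occurrence of the same adverse event with the most extreme severity", namely severe. The paragraph on maximum relationship has the same structure: "If a subject has an adverse event with unknown relationship, then the subject will be counted in the relationship category of" unknown, overridden only by another occurrence rated as a reasonable possibility.

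Two other places bear on this. SAP 11.1 says that missing safety data are not imputed. Protocol 6.1.3 says that "when the investigator has not reported a causality or deemed it not assessable, AbbVie will consider the event associated".

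**The concern.** The two sets of rules give different answers for the same event, and the SAP states neither an order of application nor a scope for each. If the worst-case rule is applied to the data first, no unknown value is left and the later paragraphs never operate. If the later paragraphs are applied, the worst-case rule is broken in those tables. Unless the text is settled beforehand, the choice falls to whoever programs the tables. The unknown rule can only leave the severe and related counts the same or lower them.

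At stake is whether the safety tables agree with each other. A reader comparing the overview with the maximum-severity table could find fewer severe subjects in the latter with nothing to explain it. For relationship, the unknown category also departs from the sponsor's stated handling of absent causality, and SAP 12.1, which lists changes from the protocol, mentions only the change in safety reporting periods.

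**Working it through.** There is no planned figure to reproduce. The check compares the rules and then runs both on assumed data.

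**Rules side by side (all from SAP 11.2.1)**

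| Item | Worst-case rule, after the overview list | Rule in the maximum-table paragraphs |
|---|---|---|
| Values covered | missing or unknown | unknown only |
| Severity goes to | severe | unknown, unless another occurrence of the event was rated severe |
| Relationship goes to | reasonable possibility | unknown, unless another occurrence was rated a reasonable possibility |
| Tables named | none | maximum severity; maximum relationship |

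The explicit clash is for values recorded as unknown, because the worst-case rule names these as well as missing values. For missing values the later paragraphs are silent.

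**Both rules applied to five assumed subjects with the same preferred term**

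| Ratings | Worst-case rule | Unknown rule |
|---|---|---|
| mild | mild | mild |
| unknown | severe | unknown |
| moderate, unknown | severe | unknown |
| severe, unknown | severe | severe |
| severe | severe | severe |

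The worst-case rule gives 4 severe and 0 unknown. The unknown rule gives 2 severe and 2 unknown. The results differ only for a subject who has an unknown rating and no occurrence rated severe. Relationship behaves in the same way, with reasonable possibility in place of severe.

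**Size per subject.** SAP 4.3 plans 100 subjects per arm, so one reclassified subject is 1/100 = 1 percentage point. If 0 to 3 subjects per arm were affected (an assumption; the documents give no number), the shift would be 0 to 3 points.

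**What would happen if the unknown rule reached the overview.** The overview comparison uses Fisher's exact test in the placebo-controlled period, and only p-values below 0.100 are shown. Assume 100 per arm, no severe events on placebo, 4 subjects with a rated severe event on adalimumab, and one more adalimumab subject whose event has unknown severity:

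- Unknown rule: 4/100 against 0/100, two-sided p = 0.121, not displayed.
- Worst-case rule: 5/100 against 0/100, two-sided p = 0.059, displayed.

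These counts are invented. They show sensitivity at small numbers and do not predict a result.

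**Against the protocol.** Protocol 6.1.3 has the sponsor treat unreported or not assessable causality as associated. This agrees with the worst-case rule for relationship and not with an unknown category. Protocol 6.1.2 defines three severity grades and gives no rule for an absent one.

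**The case against.** The strongest defence is that placement implies scope. The worst-case rule follows the overview list, and each unknown rule sits in a paragraph about one maximum table. A programmer could use worst-case coding in the overview and an unknown row in the maximum tables. This is workable, so it would be wrong to say that the two rules cannot both be programmed. But the SAP does not state that scope, and the reading itself produces the inconsistent tables.

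The same placement answers a stronger reading that a reader might infer: that the Fisher-tested severe and related counts are themselves in doubt. The sentence on Fisher's test introduces the overview list, and the rule right after that list is the worst-case one. No test is attached to the maximum tables. On the natural reading the tested counts are settled.

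On the protocol, one can argue that 6.1.3 describes the sponsor's classification while the maximum-relationship table reports the investigator's. That stands in part: 6.1.3 sets no table convention. However, the overview line on related events is also worded as the investigator's assessment, and there the SAP does use the worst-case rule, so the distinction does not explain why the two tables differ.

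Finally, affected events may be few. Protocol 6.1 asks the investigator to record severity and relationship for every event, Protocol 6.1.2 and 6.1.3 offer no unknown option, and Protocol 10.2 provides for review of the case report forms for completeness. This limits the likely size but does not remove the conflict in the text.

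**Conclusion.** The conflict is real for both severity and relationship, and nothing in the SAP reconciles it. Its consequence is limited. The overview and maximum tables may disagree if at least one treatment-emergent event has an unknown rating that is not overridden by a severe or reasonable-possibility occurrence, and if each rule is run on its own table. If there is no such event, the tables agree.

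The documents do not support saying that the tables will disagree, nor any particular number of affected subjects. They also do not support saying that the protocol requires worst-case coding of severity: Protocol 6.1.3 backs it for causality only. For severity the grounds are the unrestricted wording of the SAP's own rule and its caution. The issue concerns safety reporting, leaves primary efficacy untouched, and merits a correction because that is cheap and the choice should not be made with results in view.

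**What to change.** Before database lock, amend the SAP as follows:

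- In 11.2.1, delete the two provisions that place subjects in an unknown category, and state that the worst-case rule (severity to severe, relationship to reasonable possibility) applies in all adverse event tables.
- In 11.1, add an exception for adverse event severity and relationship to the statement on not imputing missing safety data. Without it, extending the worst-case rule would leave a second contradiction in place.
- Footnote each affected table with the number of events so coded, so that a reader can see how far the counts rest on the rule.

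Stating the scope of each rule with a footnote would also remove the ambiguity, but a subject could still be severe or related in one table and unknown in another. A single rule avoids that and, for relationship, matches Protocol 6.1.3.

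The cost is SAP wording only. Severe and related counts in the maximum tables may look slightly less favourable.

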11.2.2 Adverse Events of Special Interest

The following AEs of special interest will be summarized by number and percentage of subjects experiencing an AE of interest. The AEs of interest will be summarized and presented using primary MedDRA system organ classes (SOCs) and preferred terms (PTs) for the following AE categories:

- Any infection,
- Any serious infection,
- Any legionella infection,
- Any diverticulitis,
- Any opportunistic infection excluding oral candidiasis and TB,
- Any oral candidiasis,
- Any tuberculosis,
- Any active tuberculosis,

- Any latent tuberculosis,
- Any parasitic infection,
- Any reactivation of hepatitis B,
- Any progressive multifocal leukoencephalopathy (PML),
- Any malignancy,
- Any lymphoma,
- Any hepatosplenic T-cell lymphoma (HSTCL),
- Any non-melanoma skin cancers (NMSC),
- Any melanoma,
- Any leukaemia,
- Any malignancy other than lymphoma, HSTCL, leukaemia, NMSC or melanoma,
- Any allergic reaction including angioedema/anaphylaxis,
- Any lupus-like reactions and systemic lupus erythematosus,
- Any vasculitis,
- Any cutaneous vasculitis,
- Any non-cutaneous vasculitis,
- Any sarcoidosis,
- Any autoimmune hepatitis,
- Any myocardial infarction,
- Any cerebrovascular accident,
- Any CHF,
- Any pulmonary embolism,
- Any interstitial lung disease,
- Any intestinal perforation,
- Any intestinal stricture,
- Any pancreatitis,
- Any Stevens-Johnson Syndrome,
- Any erythema multiforme,

- Any worsening/new onset of psoriasis,
- Any demyelinating disorder,
- Any amyotrophic lateral sclerosis,
- Any reversible posterior leukoencephalopathy syndrome (RPLS),
- Any hematologic disorders including pancytopenia,
- Any liver failure and other liver event,
- Any Humira administration related medication error,
- Any injection site reaction.

Additional AEs may be considered for tabulation/summary based on recommendations from Clinical and Safety as deemed appropriate.

11.3 Analysis of Laboratory Data

Changes from baseline in continuous laboratory parameters will be summarized for each visit. The mean change from baseline will be compared between treatment groups (ADA 160/80 versus placebo) at each time point during the DB placebo-controlled period on the Safety Analysis set. Summaries of mean changes from baseline will be provided on the Any Adalimumab set for the adalimumab treatment.

Mean changes from baseline to post-baseline visits will be summarized with the baseline mean, the visit mean, change from baseline mean, standard deviation and median. The treatment group differences for mean changes from baseline will be analyzed using a one-way ANOVA and between group mean change from baseline with the 95% confidence interval, standard error, and *P* value will be presented.

Shift tables from baseline to the final value according to the normal range will be provided for each hematology, clinical chemistry parameter and urinalysis parameter (specific gravity and pH only).

For selected laboratory parameter with Common Toxicity Criteria (CTC), frequencies and percentages of subjects with post baseline lab values that are Grade 3 or above according

to the CTC toxicity criteria Version 3.0 (or later) will be summarized. Comparisons of the percentage of subjects experiencing a value meeting the criteria between treatment groups will be performed using Fisher's exact tests. Only P values ≤ 0.100 when rounded to three digits will be presented. A separate listing will be provided that presents all of the subjects and values that are CTC toxicity Grade 3 or above. For each of these subjects, the whole course of the respective parameter will be listed.

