8.1.5 Statistical Analyses of Safety

Laboratory data, adverse events (AEs), and vital signs are the primary safety parameters in this study. All safety analyses will be performed using the Safety set, which includes all subjects who enrolled into this study and received at least one dose of study drug. Treatment-emergent AEs are defined as events that begin or worsen either on or after the first dose of the study drug and within 70 days after the last dose of the study drug. An overview of treatment-emergent AEs, including AEs of special interest such as AEs leading to death and AEs leading to premature discontinuation (see details in the SAP), AEs by Medical Dictionary for Drug Regulatory Activities (MedDRA version 17.0 or later) preferred term and system organ class, AEs by maximum relationship to study drug, and AEs by maximum severity will be summarized by number and percentage. Treatment-emergent AEs will be summarized separately for the double-blind dosing period (Week 0 to Week 8) and the OL period (Week 8 to 70 days after the last dose of the study medication).

Changes in laboratory data will be described using statistical characteristics and compared between treatment groups will be performed using a one-way Analysis of Variance (ANOVA). In addition, shift tables and listings will be provided for abnormal values, whereby the normal range of the analyzing laboratory will be used. Vital signs will be analyzed similarly.

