Change from Baseline in continuous endpoints will be analyzed using Analysis of Covariance (ANCOVA) model including factor for treatment group, stratification factors and Baseline values. For analyses of changes from Baseline variables, both LOCF and observed case analyses will be performed. The LOCF analysis is considered primary for inferential purposes.

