11.0 Safety Analysis

11.1 General Considerations

Safety analyses will include reporting of adverse events, laboratory, and vital sign measurements. Safety analyses will be carried out using the Safety set for the DB placebo controlled period (Week 0 to Week 4), and will be carried out using the Any Adalimumab set for the DB/OL period of Any Adalimumab (the entire study on or after the first dose of adalimumab up to 70 days after the last dose of adalimumab, or the date subjects initiate adalimumab therapy not supplied in the context of Study M14-233). The safety analyses results through Week 4 will be presented using two treatment groups (i.e., ADA160/80 versus placebo). The safety analysis on the Any Adalimumab set will be presented for all the subjects as one adalimumab treatment group.

Comparisons between active treatment and placebo groups will be performed for the DB placebo controlled period using the safety analysis set. The safety variable will be summarized by treatment according to the treatment a subject actually received. The differences between treatment group and placebo in safety parameters will be evaluated using two-sided tests at the significance level of 0.100.

For the any adalimumab analysis Set, only summary statistics will be provided for adalimumab treatment.

Missing safety data will not be imputed.

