11.4 Analysis of Vital Signs

The following vital signs will be summarized at every visit during the study.

- Body Weight (kg)
- Blood Pressure (Systolic/Diastolic) (mmHg)
- Pulse (bpm)
- Respiratory Rate (RPM)
- Temperature ($^{\circ}$ C)

Changes from baseline in vital sign measurements will be summarized for each visit.

The mean change from baseline will be compared between treatment groups (ADA 160/80 versus placebo) during the DB placebo-controlled period on the Safety analysis set. Summaries of mean changes from baseline will be provided on the Any Adalimumab analysis set.

Mean changes from baseline to post-baseline visits will be summarized with the baseline mean, the visit mean, change from baseline mean, standard deviation and median. The treatment group differences for mean changes from baseline will be analyzed using a one-way ANOVA and the between group mean change from baseline with the 95% confidence interval, standard error, and *P* value will be presented.

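### Between-arm comparisons of mean change in laboratory and vital-sign values leave out the baseline value; adding it is a minor, nearly free gain in precision.

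*SAP*

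**What the plan says.** SAP 11.3 compares ADA 160/80 with placebo on mean change from baseline in continuous laboratory parameters at each time point of the placebo-controlled period. The model is stated as follows: "treatment group differences for mean changes from baseline will be analyzed using a one-way ANOVA". The output is a between-group difference with 95% confidence interval, standard error and P value.

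SAP 11.4 repeats this for vital signs: "The treatment group differences for mean changes from baseline will be analyzed using a one-way ANOVA".

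Protocol 8.1.5 names one-way ANOVA for laboratory changes and adds: "Vital signs will be analyzed similarly". No section adds the baseline value, or the stratification factors, to these models.

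For continuous efficacy changes, SAP 10.3 does adjust, by analysis of covariance: "ANCOVA) model including factor for treatment group, stratification factors and Baseline values". Protocol 8.1.4.2 takes the same approach. Neither document explains the difference between the two methods.

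Under SAP 11.1, between-arm safety differences are "evaluated using two-sided tests at the significance level of 0.100". Missing safety data are not imputed. The controlled comparison covers Weeks 0 to 4 only; data on the Any Adalimumab set are summarized as one group without testing.

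Mean change is not the only laboratory analysis. SAP 11.3 also plans normal-range shift tables, between-arm Fisher's exact tests on selected parameters reaching CTC Grade 3 or above, and listings. SAP 11.3.1 adds categorized liver shift tables and a listing of potentially clinically significant values.

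**The concern.** A change score uses the baseline by subtracting all of it, which amounts to assuming that follow-up rises one unit for each unit of baseline. When the true slope differs from one, this has two consequences. The residual variance is larger than it need be, so the interval is wider. And part of any chance baseline difference between the arms stays in the estimated treatment difference, as regression to the mean.

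These are the only formal between-arm comparisons of mean change in laboratory and vital-sign values. From Week 4 the placebo arm receives adalimumab, so later data cannot restore the contrast. What is at stake is some sensitivity to a small mean shift over four weeks. Nothing in the efficacy analysis is involved.

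**Working it through.** **The plan's own figures.** Neither document gives a sample size, power, standard deviation (SD) or precision target for laboratory or vital-sign comparisons. The stated 90% power (SAP 4.3) concerns Week 4 remission: 24% versus 47%, 100 per arm, two-sided Fisher's exact test at 0.05. Exact enumeration gives 90.7%, so that figure reproduces. It does not depend on the point made here.

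**Inputs.** From the documents: 1:1 allocation and 100 per arm. Assumed, because the documents do not give them: the baseline-to-visit correlation r, and k, the follow-up SD divided by the baseline SD. All results are in units of the baseline SD.

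**Formulas.**
- Per-subject variance of the change score (one-way ANOVA): 1 + k² − 2rk.
- Per-subject residual variance with the baseline as covariate (ANCOVA): k²(1 − r²).
- The first minus the second is 1 − 2rk + r²k² = (1 − rk)². The slope of follow-up on baseline is rk. ANCOVA is therefore never less precise here, apart from the one degree of freedom it uses, and the gain vanishes only when the slope is 1.
- Share of a chance baseline difference left in the ANOVA estimate: rk − 1.

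**Equal SDs (k = 1).** The variances become 2(1 − r) and 1 − r², with ratio (1 + r)/2. The 95% half-width is 1.96 × √variance × √(2/100). At r = 0.5 this is 1.96 × 1.000 × 0.1414 = 0.277 for ANOVA and 1.96 × 0.866 × 0.1414 = 0.240 for ANCOVA.

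| r (assumed) | ANOVA half-width | ANCOVA half-width | ANOVA wider by | Per-arm n at which ANCOVA matches ANOVA with 100 | Share of baseline difference left by ANOVA |
|---|---|---|---|---|---|
| 0.3 | 0.328 | 0.264 | 24.0% | 65 | −0.7 |
| 0.5 | 0.277 | 0.240 | 15.5% | 75 | −0.5 |
| 0.7 | 0.215 | 0.198 | 8.5% | 85 | −0.3 |
| 0.8 | 0.175 | 0.166 | 5.4% | 90 | −0.2 |
| 0.9 | 0.124 | 0.121 | 2.6% | 95 | −0.1 |

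The percentage column depends neither on the number per arm nor on the confidence level.

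**Simulation check** (k = 1, 100 per arm, 4000 runs). At r = 0.5, 0.7 and 0.9, the ratio of ANCOVA to ANOVA standard error was 0.869, 0.920 and 0.978; the formula gives 0.866, 0.922 and 0.975. The slope of the ANOVA estimate on the realized baseline difference was −0.50, −0.31 and −0.10. For ANCOVA it was within 0.005 of zero.

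**Size of chance imbalance.** With 100 per arm, the baseline difference has a standard deviation of √(2/100) = 0.141, so its 95% range is ±0.277. At r = 0.5 this moves the ANOVA estimate by up to about 0.5 × 0.277 = 0.14 SD.

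**Unequal SDs.** Ratio of ANCOVA to ANOVA interval width, √[k²(1 − r²)/(1 + k² − 2rk)]:
- k = 0.7, at r = 0.5, 0.7, 0.9: 0.682, 0.700, 0.636.
- k = 1.3, at r = 0.5, 0.7, 0.9: 0.955, 0.995, 0.958.
- k = 1.5, at r = 0.3, 0.5, 0.7: 0.933, 0.982, 0.999. For example, at r = 0.5 it is √(1.6875/1.75) = 0.982.

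The gain is large when follow-up varies less than baseline. It can almost disappear when follow-up varies more.

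**The case against.** The strongest reply is that nothing here is an error. Protocol and SAP agree on the method. Under randomization, one-way ANOVA on change is unbiased and its type I error is correct. The comparisons are safety screening at a two-sided 0.100 level, not powered tests. A simple unadjusted display for screening beside adjusted models for efficacy is a defensible preference. The baseline and visit means are printed beside each change, so an imbalance would be visible. All of this stands, and it is why the point is minor.

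Three stronger readings are tempting, and the documents do not support them.

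- A reader might infer that baseline imbalance biases these comparisons or produces false signals. It does not do so systematically: the carry-over is a conditional effect of chance, already part of the sampling variation that the interval covers.
- A reader might infer that these are the only formal placebo-controlled laboratory comparisons, so that a shift in transaminases or blood counts would go unseen. SAP 11.3 also tests Grade 3 or higher values between arms for selected parameters. The shift tables and the liver listing do not rely on mean change, and liver and hematologic events are of special interest under SAP 11.2.2. What is true is narrower: no other planned test compares mean change.
- A reader might take one gain figure as the cost for every parameter. The correlations and SDs are unknown. Body weight over four weeks is likely to track closely, which puts it near the 2.6% end. Entry limits on AST, ALT and WBC apply at screening and not at follow-up, which could push k above 1 and the gain toward zero.

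None of these replies gives a reason to prefer the model without baseline.

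**Conclusion.** The point holds as a small, optional improvement. The planned analysis is valid but in general less precise than it could be, and it leaves (slope − 1) times any chance baseline difference in the estimate. With equal SDs and assumed correlations from 0.3 to 0.9, the planned interval is between about 24% and 2.6% wider than the adjusted one. With unequal SDs, the width ratios examined ran from 0.636 to 0.999, so for some parameters the gain is substantial and for others negligible. These figures are illustrative and rest on assumed correlations and SDs. The conclusion that adjustment does not lose precision, beyond one degree of freedom, rests only on a linear model with a common slope and variance in both arms.

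**What to change.** In SAP 11.3 and 11.4, replace the one-way ANOVA by ANCOVA on change from baseline, with treatment and the parameter's own baseline value. Report the adjusted between-group difference with its 95% confidence interval, standard error and P value. The stratification factors may be added to match SAP 10.3, but this is not essential. Keep the planned descriptive columns, shift tables, Grade 3 or higher tests and listings as they are.

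Record the departure from Protocol 8.1.5 in SAP 12.1, which already documents another change to the safety analysis. No protocol amendment should be needed for this alone. Make the change before database lock, by which time Protocol 8.1 requires the SAP to be final.

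The cost is one extra model term per parameter and a short note in SAP 12.1. No new data are needed, since SAP 6.0 already defines the baseline value.
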